7.2 IOL IMPLANTATION SYSTEMS

8. STUDY POPULATION

All study subjects will be enrolled from the normal surgical cataract population at up to 50 sites in the U.S.A. This study will include only subjects intended to undergo bilateral primary phacoemulsification cataract extraction and IOL implantation who have either approximately 2.00 D to 3.00 D (higher-cylinder group) or approximately 1.00 D to

1.50 D (lower-cylinder control group) of corneal astigmatism requiring correction in at least one eye. The lenses to be implanted will be calculated using the TECNIS Symfony Toric Calculator and based on the combination of preoperative keratometric cylinder, the expected effect of SIA and the PCA algorithm.

Up to 634 subjects will be enrolled to achieve approximately 506 bilaterally implanted subjects, resulting in approximately 480 evaluable subjects at 6 months, 240 in the higher-cylinder group and 240 in the lower-cylinder group.

toric power IOL will determine the model group.

All patients who sign the informed consent will be enrolled in the study and subjects that meet the inclusion and exclusion criteria (Section 8.1 and 8.2) in both eyes will be offered treatment in the study. Eligibility criteria may not be waived by the investigator. Any questions regarding patient eligibility are to be discussed with JJSV prior to subject treatment. Those subjects who meet the criteria and agree to participate will be enrolled in either the higher-cylinder group or the lower-cylinder group, according to the TECNIS Symfony Toric IOL calculator. Subjects will be treated sequentially at each site until the total recruitment goals for each lens model are met.

The eye implanted with the highest

8.1 INCLUSION CRITERIA:

Note: All criteria apply to each eye unless otherwise indicated:

- Minimum 22 years of age
- Bilateral cataracts for which phacoemulsification extraction and posterior chamber IOL implantation have been planned
- Preoperative keratometric cylinder of:
 - Approximately 2.00 D to 3.00 D resulting in a calculated lens power (using the web-based TECNIS Symfony Toric IOL Calculator) that requires implantation of a ZXT300 or ZXT375 IOL in at least one eye for the subject to be eligible for the higher-cylinder group, or

- Approximately 1.00 D to 1.50 D resulting in a calculated lens power (using the web-based TECNIS Symfony Toric IOL Calculator) that requires implantation of a ZXT150 IOL in at least one eye for the subject to be eligible for the lower-cylinder group
- The eye with the higher toric power IOL will determine the model group
- The fellow eye must be the same or a lower toric power
- Predicted residual refractive cylinder based on the TECNIS Symfony Toric IOL calculator, taking surgically-induced astigmatism into account and using the posterior corneal astigmatism option, must be ≤0.50 D for all toric eyes
- Clear intraocular media other than cataract in each eye
- Availability, willingness, ability and sufficient cognitive awareness to comply with examination procedures and study visits
- Ability to understand, read and write English in order to consent to study participation and complete study questionnaires
- Signed informed consent and HIPAA authorization

8.2 EXCLUSION CRITERIA:

Note: All criteria apply to each eye

- Irregular corneal astigmatism
- Any clinically-significant corneal pathology/abnormality other than regular corneal astigmatism
- Previous corneal surgery
- Recent ocular trauma or intraocular surgery that is not resolved/stable or may affect visual outcomes
- Any clinically-significant pupil abnormalities (non-reactive, fixed pupils, or abnormally-shaped pupils)
- Subjects with conditions associated with increased risk of zonular rupture, including capsular or zonular abnormalities that may lead to IOL decentration, including pseudoexfoliation, trauma, or posterior capsule defects
- Known ocular disease or pathology that, in the opinion of the investigator, may affect visual acuity or require surgical intervention during the course of the study (macular degeneration, cystoid macular edema, diabetic retinopathy, uncontrolled glaucoma, etc.)
- Concurrent participation or participation during 30 days prior to preoperative visit in any other clinical study
- Planned monovision correction
- Patient is pregnant, plans to become pregnant, is lactating or has another condition associated with the fluctuation of hormones that could lead to refractive changes

9. INVESTIGATOR APPROVAL

9.1 INVESTIGATOR QUALIFICATIONS

JJSV will select ophthalmic surgeons who have completed a residency in ophthalmology (or its documented equivalent) and are licensed to practice medicine and perform surgery at his/her investigative site.

. All sites are required to have

adequate staff support for reporting and subject follow-up, as well as the necessary instrumentation to conduct study testing.

9.2 INVESTIGATOR OBLIGATIONS

Investigators are required to fulfill the following obligations:

- Conduct the study in accordance with the relevant and current protocol. Investigator will only make changes to a protocol after notifying and obtaining approval from JJSV, the FDA, and the Institutional Review Board (IRB), except when necessary to protect the safety, rights or welfare of subjects
- Personally conduct and supervise the study
- Maintain a list of appropriately qualified persons to whom the investigator has delegated significant study-related duties
- Be responsible for protecting the rights, safety and welfare of subjects under the investigator's care
- Maintain confidentiality as required by HIPAA or similar laws and regulations
- Shall not obtain written informed consent of any subject to participate or allow any subject to participate before FDA and IRB approval are obtained
- Document in each subject's case history that informed consent was obtained prior to participation in the study
- Report to JJSV any adverse experiences and/or device defects or malfunctions that occur during the course of the study in accordance with applicable laws and regulations
- Maintain adequate and accurate records in accordance with applicable laws and regulations and make available all study documents and subject medical records for inspection by either JJSV, duly authorized regulatory agencies (e.g., FDA, PMDA, Health Canada, etc.) and/or the IRB
- Submit progress reports on the study to JJSV and the reviewing IRB at regular intervals, but no less often than yearly as required by the FDA Guidance Document on PAS "Procedures for Handling Post-Approval Studies Imposed by PMA Order," dated June 15, 2009.

- Ensure the IRB that is responsible for initial and continuing review of the study complies with applicable laws and regulations
- Report all changes in research activity and all unanticipated problems involving risks to subjects to the IRB and JJSV
- Submit a final report to JJSV and reviewing IRB within 3 months after termination or completion of the study or the investigator's part in the study
- Provide sufficient accurate financial information to JJSV to allow JJSV to submit complete and accurate certification or disclosure statements as required by 21CFR54. Promptly update this information if any relevant changes occur during the course of the study or for up to one year following completion of the study
- Comply with all other obligations of clinical investigators and requirements according to all applicable FDA regulations, all other applicable laws and regulations and all conditions of approval imposed by the reviewing IRB and FDA
- Ensure that all associates, colleagues and employees assisting in the conduct of the study are adequately informed about the protocol, the study devices, their study-related duties and functions and agree to fulfill their obligations in meeting the above commitments.

Investigators shall provide adequate time and resources to conduct and report on the study. The Investigator, or delegate, shall notify JJSV of any change in the conduct of the study including changes in study personnel assigned to the study project, location of the study device(s), or maintenance of study records, etc.

9.3 INVESTIGATOR APPROVAL

It is the responsibility of the investigator to obtain prospective approval of the study protocol, protocol amendments or changes, informed consent forms and other relevant documents (e.g., advertisements) from the IRB.

sites will obtain IRB approvals and fulfill

any other site-specific regulatory requirements.

The investigator is required to report to JJSV within five working days any withdrawal of approval by the reviewing IRB for his/her participation in the investigation.

By signing the study documents, the investigator agrees to conduct this study according to the obligations above and all other applicable regulatory and legal requirements.

10. STUDY TIMELINE

[figure not shown]

11. EXPERIMENTAL PLAN

11.1 OVERVIEW

This study will be conducted in accordance with U.S. Code of Federal Regulations, the Declaration of Helsinki, ISO 14155:2011 and all other applicable laws and regulations. The study will not begin until regulatory and IRB approvals have been obtained.

This study will be a prospective, multicenter, bilateral, non-randomized, open-label, comparative, 6-month clinical study conducted at up to 50 U.S. sites. Subjects will be bilaterally implanted with Symfony lenses.

[figure not shown]
month and 6 months following the second-eye surgery. A 1-year examination will be required only if the subject reports any of the 3 bothersome visual symptom items of interest at the 6-month examination, or if the subject experiences an IOL repositioning procedure due to IOL misalignment during the study.

Key preoperative data include ocular health and history, visual acuities, manifest refraction, keratometry, biomicroscopic slit-lamp findings, ocular symptoms and biometry. The operative visit will include standard procedures for cataract surgery and

IOL implantation. Key postoperative data collection includes non-directed visual symptoms, questionnaires, distance visual acuities, manifest refraction, keratometry, slit-lamp findings and adverse events. A chart summary of all examination procedures required at each study visit is provided in **Appendix A**.

[figure not shown]
11.2 VISIT SCHEDULE

The study visit schedule for all study subjects is outlined below in **Table 4**. Additional visits may be conducted at the discretion of the investigator; however, routine follow-up visits without reports of ocular adverse event(s) or spontaneous reports of any of the 3 bothersome visual symptom items of interest are not considered study visits and will not be reported in the study database.

11.3 **PREOPERATIVE PROCEDURES**

Subjects will be considered eligible for treatment only after the current IRB-approved informed consent form is signed and all eligibility criteria are met. The informed consent form must be signed before any study-specific examinations are performed, and this must be documented in the source documents. An Authorization for Use/Disclosure of Health Information Form (HIPAA authorization) or similar medical treatment privacy law documentation must also be signed.

IOL calculator) of the toric power lens choice for each eye of each subject is required.

Preoperative testing to be performed includes the following:

- Informed consent documentation
- Subject demographic information
- Ocular history, including presence of ocular pathology for each eye
- Potential best-corrected distance visual acuity for each eye (Note: Snellen 20/30 or better is recommended for study inclusion; may be performed by surgeon estimation)
- Monocular uncorrected distance visual acuity (Snellen) for each eye
- Monocular best corrected distance visual acuity (Snellen) for each eye
- Manifest refraction (Snellen) for each eye
- Keratometry for each eye by keratometer only (no Sim-K allowed)
- Intraocular pressure for each eye
- Ocular medications for each eye
- Cataract type and density for each eye
- Fundus exam for each eye (dilated with ophthalmoscopy or undilated with a wide-field retinal imaging system, e.g., Optomap. The same method should be used for pre- and postoperative examinations)
- Medical and lens findings for each eye from a biomicroscopic slit-lamp exam
- Axial length, vertex distance, spherical equivalent IOL power and spherical equivalent targeted refraction (emmetropia, within ±0.50 D) for each eye using the investigator's preferred biometry method (IOLMaster, LenStar, or ultrasound)
- A-constant or Surgeon Factor used for spherical equivalent IOL power determination for each eye
- Surgeon-estimated surgically-induced astigmatism (SIA) and planned incision location for each eye
- Documentation of the TECNIS Symfony Toric IOL calculator choice of ZXT toric power for each eye and corresponding residual refractive cylinder and axis, as well as documentation of inclusion of the optional posterior corneal astigmatism algorithm

• PRVSQ Subject Questionnaire (Appendix B)

LENS POWER CALCULATIONS AND IOL SELECTION:

In order to verify subject eligibility and to optimize toric IOL selection and axis placement,

[figure not shown]
investigators will use the web-based TECNIS Symfony Toric IOL calculator (www.TecnisToricCalc.com) to determine the appropriate IOL model for each eye. Note that the TECNIS Symfony Toric IOL calculator provides toric IOL options based on predicted astigmatism, i.e., the vector sum of pre-existing corneal astigmatism and the expected effect of SIA. For this study, subjects are to have corneal astigmatism in at least one eye that, when taking SIA into account and using the PCA algorithm, has approximately 2.00 D to 3.00 D (higher-cylinder group) or 1.00 D to 1.50 D (lower-cylinder group) of corneal astigmatism to be corrected, and subjects must qualify for implantation of the suitable toric IOL by the TECNIS Symfony Toric IOL calculator.

Predicted residual refractive cylinder must be ≤ 0.50 D for all toric eyes. For all subjects, the IOL model selections chosen by the investigator via the TECNIS Symfony Toric IOL calculator are to be printed and maintained as source documentation.

11.4 STUDY LENS SUPPLY

11.5 OPERATIVE PROCEDURES

The investigator should use his or her standard, small-incision, cataract extraction surgical technique. All lenses should be folded for implantation and inserted into the capsular bag using one of the JJSV-validated insertion systems.

Following lens insertion, Symfony Toric IOLs are to be precisely aligned with the intended axis of placement using the imaginary line formed by the axis orientation marks at each of the haptic/optic junctions of the IOL, identifying the flat meridian of the optic. Special care should be taken to ensure proper positioning of the Symfony Toric IOL at the intended axis following viscoelastic removal and/or inflation of the capsular bag at the end of the surgical case. All viscoelastic must be carefully removed from the capsular bag. Residual viscoelastic and/or over-inflation of the bag may allow the lens to rotate, causing misalignment of the Symfony Toric IOL from the intended axis.

Operative case report forms will collect the following information:

- Date of surgery
- Operative eye
- IOL model, power and serial number
- Use of intraoperative wavefront analysis
- Incision location
- Surgical complications
- Other surgical procedures
- IOL placement (e.g., within capsular bag, proper alignment, etc.)
- Wound closure (e.g., suture required)
- Adverse events

- Non-directed subject question responses at every visit.
- PRVSQ questionnaire: 1-month, 6-month and 1-year visits. Following completion of the questionnaire by the subject, the questionnaire is to be reviewed by the site personnel for reports of very or extremely bothersome visual symptoms of interest (halos, glare or starbursts) that impact daily living under overall conditions.
- Keratometry: 1-month, 6-month and 1-year visits
- Monocular uncorrected distance visual acuity at 4 m (Snellen or ETDRS): 1-month, 6-month and 1-year visits
- Manifest refraction (Snellen or ETDRS): 1-month, 6-month and 1-year visits; manifest refraction is to be performed using the Maximum Plus refraction method as detailed in **Appendix C**.
- Monocular best corrected distance visual acuity at 4 m (Snellen or ETDRS): 1-month, 6-month and 1-year visits
- Medical and lens findings from biomicroscopic slit-lamp exam: 1-month, 6-month and 1-year visits; findings of aqueous cells and flare, corneal edema, posterior capsule striae, posterior capsular opacification and IOL glistenings are to be rated using standardized grading scales provided in **Appendix D**.
- Ocular medications: In the event of a serious and/or device-related adverse event.
- Intraocular pressure: 1-month, 6-month and 1-year visits
- Fundus exam, if medically indicated
- Occurrence of Nd:YAG capsulotomy(ies)
- Occurrence of any adverse events

11.7 UNSCHEDULED VISITS

A visit is considered an unscheduled study visit when it occurs other than at the specified 1-day, 1-week, 1-month or 6-month study visits AND at which a serious or device-related adverse event is reported OR if the subject has a spontaneous report of any of the 3 visual symptom items of interest (halos, glare or starbursts) after the 1 month postoperative visit.

Testing to be performed at an unscheduled visit due to a serious or device-related adverse event is at the discretion of the Investigator. If the event results in an IOL

repositioning procedure (secondary surgical procedure), keratometry is to be performed and the PRVSQ questionnaire is to be administered PRIOR to the IOL repositioning.

At any unscheduled visit where the subject spontaneously reports any of the 3 visual symptom items of interest (halos, glare or starbursts), the PRVSQ questionnaire is to be administered.

Following completion of a PRVSQ questionnaire by the subject, the questionnaire is to be reviewed by the site personnel

.

At any unscheduled visit where any of the 3 **and the second secon**

Data to be collected on unscheduled visit forms include:

- Serious or device-related adverse event, date of onset, classification, prognosis and treatment
- Non-directed subject question
- PRVSQ questionnaire in the event of a spontaneous report of any of the 3 visual symptoms of interest (_______) or prior to an IOL repositioning procedure
- Manifest refraction (Snellen or ETDRS) if a serious or device-related event occurs or if any of the 3 visual symptom items of interest

are reported via PRVSQ

 Uncorrected and best-corrected monocular distance visual acuity (Snellen or ETDRS) - if a serious or device-related event occurs or if any of the visual symptom items of interest

are reported via

PRVSQ

 Keratometry - if a serious or device-related event occurs or if any of the visual symptom items of interest (

reported via

PRVSQ

- Slit-lamp examination findings of aqueous cells and flare, corneal edema, posterior capsule striae, posterior capsular opacification and IOL glistenings are to be rated using standardized grading scales provided in **Appendix D**.
- Fundus exam, if performed
- Ocular medications if a serious or device-related event occurs

11.8 EXIT OF SUBJECTS

An Exit Case Report Form will be completed for all subjects, either when they complete the study or if they exit early.

It is the responsibility of the investigator to provide complete follow-up data to JJSV for each subject, and every attempt will be made to gather that complete follow-up data for all subjects enrolled as missing data can have a negative effect on the study results. Patients who would be traveling, relocating or otherwise unavailable for postoperative follow-up visits should not be chosen for this clinical study.

SUBJECT FOLLOW-UP

[figure not shown]
To minimize subjects lost to follow-up, compensation will be provided for the subject's time and participation in the study at the 1- and 6-month postoperative exams, as well as the 1-year visit, if required. Additionally, sites will be compensated for completion of the 1-day, 1-week, 1- and 6-month exams as well as the 1-year visit, if required. Sites will be provided frequent listings of upcoming 1-month, 6-month and 1-year visits. It is anticipated that at least 95% of implanted subjects will be available for the 6-month study visit (i.e., no more than a 5% lost-to-follow-up rate at 6 months postoperatively).

SUBJECT EARLY EXIT

Subjects will be discontinued from the study if the study lens is removed or if the subject dies. Subjects will be considered "lost-to-follow-up" from the study only if irretrievably lost for unavoidable reasons (e.g., subject moved/unable to locate, subject uncooperative/refuses further study participation, subject ill/unable to travel).

possible, have the subject return for a final study visit.

If a subject is exited early from the study, the investigator will complete an Exit Case Report Form indicating the reason for study exit. In the event of a lens removal or other serious adverse event, the subject may be exited from the study; however, effort should be made by the investigator to follow the subject until resolution of the adverse event. In this situation, additional information will be documented in the SAE/ADE form, not on an Unscheduled Visit form. Following study completion or early exit, all study subjects are to be instructed to undergo regular eye examinations at least yearly and also to return to their doctor if any eye complications are experienced in the interim.

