Bilateral cataracts with corneal astigmatism in at least 1 eye of approximately 2.00 D to 3.00 D (higher-cylinder group) or approximately 1.00 D to 1.50 D (lower-cylinder group) based on the combination of preoperative keratometric cylinder, the expected effect of surgically-induced astigmatism (SIA), use of the optional posterior corneal astigmatism (PCA) algorithm and TECNIS Symfony Toric Calculator outcomes of ZXT300 or ZXT375 (higher-cylinder group) or ZXT150 (lower-cylinder group).

Number of subjects:Up to 634 subjects will be enrolled to achieve
bilateral implantation in approximately 506 subjects,
resulting in approximately 240 evaluable subjects in
the higher-cylinder group and 240 evaluable subjects
in the lower-cylinder group at 6 months

This is a bilateral study; both eyes must be implanted with a TECNIS Symfony IOL, either toric (Models ZXT150, ZXT225, ZXT300 or ZXT375) or non-toric (TECNIS Symfony Extended Range of Vision IOL, Model ZXR00). Each eye may have a different TECNIS Symfony IOL implanted, as determined by the surgeon and the TECNIS Symfony Toric IOL calculator; however, at least one eye must be implanted with either a Symfony Toric IOL Model ZXT150 (lower-cylinder group) or a Model ZXT300 or ZXT375 (higher-cylinder group) and the fellow eye must have the same or a lower toric power. The eye with the highest toric power IOL will determine the model group.

NOTE: No site may enroll more than 25% of the enrollment total.

Inclusion Criteria (all study criteria apply to each study eye unless otherwise indicated):

- Minimum 22 years of age
- Bilateral cataracts for which phacoemulsification extraction and posterior chamber IOL implantation have been planned
- Preoperative keratometric cylinder of:
 - Approximately 2.00 D to 3.00 D resulting in a calculated lens power (using the web-based TECNIS Symfony Toric IOL Calculator) that requires implantation of a ZXT300 or ZXT375 IOL in at least one eye for the subject to be eligible for the higher-cylinder group, or

- Approximately 1.00 D to 1.50 D resulting in a calculated lens power (using the web-based TECNIS Symfony Toric IOL Calculator) that requires implantation of a ZXT150 IOL in at least one eye for the subject to be eligible for the lower-cylinder group
- The eye with the higher toric power IOL will determine the model group
- The fellow eye must be the same or a lower toric power

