13. PROTOCOL CHANGES AND PROCEDURES

If the investigator desires to modify any procedure and/or the design of the study, he or she must contact and obtain consent from JJSV regarding the proposed changes prior to implementation. Any modifications (including additional data collection) require approval by the FDA and all other appropriate regulatory agencies, as well as approval of the governing IRBs prior to implementation.

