21.1 ANALYSIS POPULATION

For the primary endpoint, the primary analysis population will be all bilaterally-implanted subjects having available data at the 6-month visit, with data reported separately for the higher- and lower-cylinder groups. Data will also be reported for all subjects, including bilateral subjects and those with only one eye implanted (having a phakic lens, a cataract or other IOL in the fellow eye).

In addition to the primary population analyses discussed above, additional analyses will also be performed for the primary endpoint to evaluate the

at the six-month visit who did not undergo repositioning or IOL removal.

For other questionnaire items, bilaterally-implanted subjects with data at six months postoperative will be used for analysis. Refraction, monocular visual acuity, medical/lens findings and adverse event data will be reported for primary eyes (first eye implanted) and fellow eyes. Data will be reported separately for the higher-cylinder group (ZXT300, ZXT375) and the lower-cylinder control eyes (ZXT150).

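### Do the two statements on lens removal in Protocol 11.8 leave it open who is counted in the primary symptom rates?

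*Protocol*

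**What the plan says.** Protocol 11.8, under Subject Early Exit, makes two statements about removal of a study lens:

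- "Subjects will be discontinued from the study if the study lens is removed or if the subject dies".
- "In the event of a lens removal or other serious adverse event, the subject may be exited from the study". The sentence continues that "effort should be made by the investigator to follow the subject until resolution of the adverse event", and the section sends the further information to the SAE/ADE form.

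Between them stands a sentence whose opening is missing. Its visible end asks sites to "have the subject return for a final study visit".

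For the primary endpoints, Protocol 21.1 and SAP 2.1 give the same definition: "the primary analysis population will be all bilaterally-implanted subjects having available data at the 6-month visit". Protocol 21.1 also plans additional primary-endpoint analyses. That sentence is cut and ends "at the six-month visit who did not undergo repositioning or IOL removal". SAP 2.1 breaks off where it turns to the final report.

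The study is bilateral: the Synopsis states that "both eyes must be implanted with a TECNIS Symfony IOL". Protocol 11.8 speaks of the study lens in the singular.

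**The concern.** On a literal reading, the first statement obliges a site to discontinue a subject after lens removal and the second allows the site to choose. With up to 50 sites, one might exit the subject and another might keep the subject to 6 months. Membership of the primary population depends on having 6-month data, so the denominators of both primary rates could depend on site habit. Whether the fellow eye has 6-month data could depend on it too.

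Removal may also be linked to the outcome. Explants related to visual symptoms are a listed endpoint (Protocol 6.2), so subjects lost this way could be more symptomatic than the rest, and losing them could lower the observed rate. Finally, in a bilateral study the visible sentence does not say whether removal from one eye is enough to trigger the rule.

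**Working it through.** **The text**

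1. The first sentence deals with removal and death, and states what happens to the subject.
2. The second deals with a mixed class: removal together with other serious adverse events. Exit is not mandatory for the other events, so a permissive verb suits the class as a whole. The weight of the sentence falls on what follows: pursue the event to resolution and record it on the SAE/ADE form. Protocol 12.5 is in line with this, since subjects exited for a serious or device-related event are still followed until the outcome is known.
3. The closing words of the additional analysis in Protocol 21.1 might suggest that some subjects with a removal have 6-month data, which would favour the permissive wording. They do not show it. Repositioned subjects stay in the study (Protocol 11.6 follows them to 1 year), so the exclusion has work to do through repositioning alone. A removal after the 6-month questionnaire would also leave 6-month data under either wording.
4. On one eye or both, the Synopsis lists the fellow-eye models under the heading of other study lenses. A lens in either eye can therefore be read as a study lens, although 11.8 does not say so.

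**Inputs**

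- 240 evaluable subjects per group, an assumed rate of 20%, and a two-sided 95% interval (Protocol 21.5, SAP 7).
- Removals per group, k: not in the documents. The values 2, 5 and 8 are assumptions.

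**The plan's own precision**

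The half-width is z × sqrt(0.20 × 0.80 / 240), and sqrt(0.16/240) = 0.02582.

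- At 95%: 1.96 × 0.02582 = 5.06 points.
- At 90%: 1.645 × 0.02582 = 4.25 points.

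The plan states 4.2 points, which fits a 90% interval. That is a separate matter. The yardstick here is 5.06, and every shift in the table below is also smaller than 4.2.

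**Shift in one group's rate**

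If subjects with a removal are exited, the rate is 48/240 = 20.00%. If k such subjects are kept, each counts only on his or her own 6-month questionnaire. The bounds are 48/(240 + k), where none is symptomatic, and (48 + k)/(240 + k), where all are.

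| k | None symptomatic | Shift | All symptomatic | Shift |
|---|---|---|---|---|
| 2 | 48/242 = 19.83% | -0.17 | 50/242 = 20.66% | +0.66 |
| 5 | 48/245 = 19.59% | -0.41 | 53/245 = 21.63% | +1.63 |
| 8 | 48/248 = 19.35% | -0.65 | 56/248 = 22.58% | +2.58 |

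If about 20% of the retained subjects are symptomatic, the rate does not move.

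**Shift in the difference between groups**

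Start from 20.00% in both groups and apply the same bound to each.

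- Five removals in each group: 0.00 points at either bound.
- Five against one, none symptomatic: 48/245 - 48/241 = 19.59 - 19.92 = -0.33 points.
- Five against one, all symptomatic: 53/245 - 49/241 = 21.63 - 20.33 = +1.30 points.

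The 95% half-width for the difference is 1.96 × sqrt(2 × 0.16 / 240) = 7.16 points.

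**The unfavourable case from the other side**

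Suppose the 240 include k symptomatic subjects who had a removal and then drop out. The rate becomes (48 - k)/(240 - k).

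- k = 1: 47/239 = 19.67%, a fall of 0.33 points.
- k = 5: 43/235 = 18.30%, a fall of 1.70 points.
- k = 12: 36/228 = 15.79%, a fall of 4.21 points.

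The last case needs a quarter of all symptomatic subjects (12 of 48) to have a lens removed, and the fall is still below 5.06 points.

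**The case for a change.** The strongest reply is that both sentences are complete and visible, that the second names lens removal first and explicitly, and that a site could fairly rely on either. Removal may be tied to symptoms, so any loss is potentially informative. Following an event to resolution on the SAE/ADE form does not supply a 6-month PRVSQ. Aligning the wording would take only a sentence or two.

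Much of this stands. The verbs do differ for the same event, the one-eye question is not answered in so many words, and the direction of a possible bias is plausible.

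What does not stand is the step from there to an unclear primary analysis. The population rule asks only whether 6-month data exist, so the analyst can apply it without choosing between the two sentences. The visible end of the additional analyses excludes removals, so as far as can be seen that result is the same under both readings. Explants related to visual symptoms are reported as a rate of their own (Protocol 21.3, SAP 5.4), and an exit form records the reason for each early exit, so such subjects do not vanish from the report. Text is missing from 11.8, 21.1 and SAP 2.1, so it cannot be claimed that the plan lacks a rule for them; the missing text might even separate the two cases.

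**Conclusion.** The concern is right about the wording and does not carry through to the analysis. Protocol 11.8 uses a mandatory and a permissive verb for the same event. The two sentences should be brought into line when the protocol is next revised, and no view is taken here on which should stand. This does not justify an amendment of its own, since Protocol 13 provides that "Any modifications (including additional data collection) require approval by the FDA", and IRB approval is needed as well. Aligning the verbs would bring no better estimator, population or table.

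Under 2 to 8 assumed removals per group, the single-group rate shifts by -0.65 to +2.58 points at the extremes, inside a half-width of 5.06. With five removals against one, the group difference moves by -0.33 to +1.30 points, inside a half-width of 7.16. These sizes rest on assumed removal counts and on the plan's 20% rate. The visible primary analysis reports rates with confidence intervals and gives no test or margin that such a shift could tip. No conclusion is shown to change.
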